**Table 5 Study Procedures and Assessments**

Study Visits 	Screening Visit 1	Day 1 Visit 2*	Day 16-22 Visit 3*	End of Study/Early Withdrawal visit Day 30-36 Visit 4
Informed consent 	X			
Inclusion/exclusion criteria	X	X		
Randomisation		X		
Demographics 	X			
Medical history 	X			
Prior therapies 	X			
Concomitant therapies 	X	X	X	X
Physical examination 	X	X	X	X
Vital signs 	X	X	X	X
ECG 	X			X
Haematology 	X	X	X	X
Blood chemistry 	X	X	X	X
Blood PK sampling 		X	X	
Urinalysis 	X	X	X	X
Urine PK sampling 		X	X	
Pregnancy test 	βHCG (blood test)	Urinary hCG	Urinary hCG	βHCG (blood test)
Somatostatin Receptor Scan 	X			
 Ga-OPS202 PET/CT imaging 		X	X	
Adverse events 	X	X	X	X
Compliance 		X	X	

[1] **Study visits:** Screening Visit up to 2 weeks; Visit 3 will occur between Day 16 and Day 22, Follow-up Visit to be performed 2 weeks after Visit 3. \* The subjects may be hospitalised overnight at Visit 2 and Visit 3 at the discretion of the investigator. On Day 2 (prior to discharge if subject hospitalised), the subject should undergo the following examinations: review of AEs, new or changed concomitant medications, vital signs, physical examination, haematology, biochemistry, urinalysis.

[2] **Informed consent:** Must be obtained prior to undergoing any study specific procedures and may occur prior to the 2-week screening period

[3] **Demographics:** Age, sex and self-reported race/ethnicity

[4] **Medical history and prior therapies:** To include clinically significant diseases, surgeries, cancer history (including prior NET Therapies) and all relevant medications

[5] **Concomitant medications:** Dose and indication will be recorded from 3 months prior to the start of study treatment, at study entry and at each visit. Once the subject has withdrawn from the study, concomitant medications and treatments should be recorded until all study treatment-related toxicities have resolved;

[6] **Physical examination:** Major body systems, body weight, height (screening visit only), vital signs 0.5, 1, 2 and 4 hours post-injection (supine and standing systolic and diastolic blood pressure, heart rate), body temperature, respiratory rate

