## 6 DIAGNOSTIC IMAGING OF SUBJECTS

### 6.1 Study Imaging Product

#### 6.1.1 Ga-OPS202

At Screening, subjects will be allocated a subject number. Following confirmation of eligibility for the study, subjects will be randomised to one of the following sequence of Ga-OPS202 peptide mass dose/ radioactivity dose ranges:

- Arm A: 5-20 µg/ 40-80 MBq at Visit 2 and 30-45 µg/ 100-140 MBq at Visit 3

or

- Arm B: 5-20 µg/ 100-140 MBq at Visit 2 and 30-45 µg/ 160-200 MBq at Visit 3

or

- Arm C: 5-20 µg/ 160-200 MBq at Visit 2 and 30-45 µg/ 40-80 MBq at Visit 3

Ga-OPS202 is a diagnostic medicinal product with three main components, namely:

- Ga, a positron emitter radionuclide with a half-life of 68 min
- NODAGA, a chemical chelator group, and
- JR11, an antagonist somatostatin analogue that binds to sst2 receptors

OPS202 (cold kit) is available for clinical trials in a 50 µg peptide dose vial, and is radiolabeled using a Ge/Ga-generator. Due to the short half-life (68 min) of the Ga radioisotope, on-site generation of Ga-labeled radiopharmaceuticals is mandatory. The Ga is eluted initially from the generator with hydrochloric acid and the eluate combined with the reconstituted peptide kit preparation. The radiolabelling occurs at room temperature. The product then undergoes radiopharmaceutical quality control (see Preparation, Radiolabeling and QC manual).

The radiolabelled OPS202 (Ga-OPS202) consists of 50 µg of peptide in a total volume of 6 mL (8.33 µg/mL). Sampling of 0.5 mL for QC yields 5.5 mL solution from which the volume to be administered is withdrawn. This volume to be injected is calculated to obtain the target peptide mass dose and the desired radioactivity dose.

The calculation of the volume takes into account the different components that determine the final radioactivity dose, the subject will be exposed to, in particular:

- The amount of Ga eluted from the generator which depends on the latter half-life
- The time elapsed between OPS202 (cold kit) radiolabelling and the injection of Ga-OPS202 to the subject (decay of Ga), the variation of which is a tool to adjust the final peptide/radioactivity dose required to be injected
- The required peptide mass dose and radioactivity dose of Ga-OPS202 to be injected.

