For the safety parameters measured at each visit (ECG, laboratory data, vital signs, physical examinations), allocation to each combination of injected peptide/radioactivity dose range will follow the rule below:

- A unique baseline value will be defined per subject, as the last measurement collected prior to the first IIP administration
- For the post-baseline visits, assessments will be allocated to the last dose of ^{68}Ga -OPS202 received, based on date/time of assessment.

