Laboratory data (serum haematology and biochemistry panels, urinalysis) will be listed in SI units and abnormal values will be flagged (high [H], low [L], clinically significant [C], NCI-CTC grade (G)) where applicable. Any unscheduled laboratory assessments will be flagged [U] in the listings.

- **Haematology and Biochemistry**

For haematology and biochemistry parameters, the baseline will be defined as the last measurement collected prior to the first IIP administration.

For haematology and biochemistry parameters, summary statistics, by combination of injected peptide/radioactivity dose range and overall, will be presented at each scheduled assessment (Baseline, Post-dose, EOS/EW) for actual values and changes from baseline.

Shift tables for haematology and biochemistry parameters will be presented of the number and percentage of subjects with low, normal or high values.

Haematological and biochemistry toxicities will be recorded and graded according to the NCI-CTC criteria, Version 4.03, dated 14 June 2010. The NCI CTC grade (0 to 4) of haematology and biochemistry by visit and by subject and will be listed in Section 16.2.8.

Listings of the laboratory parameters (as described in SAP Appendix 2 section 14.3.4) will include listings of NCI-CTC Grade 3 and 4 haematological toxicities, listings of NCI-CTC Grade 3 and 4 biochemical toxicities and listings of out of range biochemistry parameters that could not be graded using NCI-CTC grade (below Lower Limit of Normal range (LLN) – normal – above Upper Limit of Normal range (ULN)).

Those listings will be presented by combination of injected peptide/radioactivity dose range, subject number and visit.

- **Urinalysis**

For categorical urinalysis data (absent/trace/positive of protein, ketones, bilirubin, blood, urobilinogen, nitrites, leukocyte esterase and glucose) frequency tables, by combination of injected peptide/radioactivity dose range, will be presented at each scheduled assessment (Baseline, post-dose, EOS/EW).

For continuous urinalysis data (pH and specific gravity), summary statistics, by combination of injected peptide/radioactivity dose range, will be presented at each scheduled assessment (Baseline, post-dose, EOS/EW) for actual values and changes from baseline.

3.2.2.3 *Vital signs*

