Vital signs (body temperature, supine and standing blood pressure and heart rate, respiratory rate) and body weight will be listed by each assessment by combination of injected peptide/radioactivity dose range and subject. Any unscheduled vital signs will be flagged [U] in the listing.

Baseline values will be defined as the last vital signs measurement collected prior to the first IIP administration.

Summary statistics by combination of injected peptide/radioactivity dose range and overall will be presented at each scheduled assessment for actual values and changes from baseline.

Following assessment will be analysed: Baseline, 0.5h Post-dose, 1h Post-dose, 2h Post-dose, 4h Post-dose, EOS/EW.

3.2.2.4 *ECG*

ECG results will be listed at each assessment (Screening, EOS/EW) by combination of injected peptide/radioactivity dose range and subject. Any unscheduled ECG will be flagged [U] in the listings.

Baseline will be defined as the first ECG measurement collected prior to the first IIP administration.

For continuous ECG parameters (heart rate, RR duration, PR duration, QRS duration, QT duration, QTc Bazett, QTc Fridericia, QTc manual) summary statistics, by combination of injected peptide/radioactivity dose range and overall, will be presented at each scheduled assessment (EOS/EW) for actual values and changes from baseline.

For interpretation of clinical significance (within normal limits / abnormal, not clinically significant / abnormal, clinically significant / not evaluable), a frequency table will be presented, by combination of injected peptide/radioactivity dose range and overall, at each post-dose assessment (EOS/EW) as well as the changes from baseline with the following categories: improved, stable, worsened, clinically significant worsening.

3.2.2.5 *Physical examination*

Physical examination (normal, abnormal, specification for abnormal result) will be listed by combination of injected peptide/radioactivity dose range, subject number and visit. Any unscheduled physical examination will be flagged [U] in the listings.

3.2.3 *Missing data and outliers*

3.2.3.1 *Missing data*

- Efficacy endpoints

No imputations will be made for missing data.

- Safety endpoints

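### Laboratory and vital-sign changes are tabulated by dose combination but all measured from one value before the first injection, so every 30-45 µg change also includes whatever shifted in the 15-21 days since then

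*SAP*

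**What the plan says.** SAP 3.2.2 sets the rule for all visit-based safety parameters: "A unique baseline value will be defined per subject, as the last measurement collected prior to the first IIP administration". It then assigns later values: "For the post-baseline visits, assessments will be allocated to the last dose of" study product received.

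The parameter sections repeat the rule. SAP 3.2.2.2, on haematology and biochemistry, says "the baseline will be defined as the last measurement collected prior to the first IIP administration", and its summaries by combination "will be presented at each scheduled assessment (Baseline, Post-dose, EOS/EW) for actual values and changes from baseline". SAP 3.2.2.3 says "Baseline values will be defined as the last vital signs measurement collected prior to the first IIP administration", and lists the timepoints: "Following assessment will be analysed: Baseline, 0.5h Post-dose, 1h Post-dose, 2h Post-dose, 4h Post-dose, EOS/EW". That list has no slot for a pre-injection value at Visit 3. Under the general rule in SAP 3.2.2, the laboratory shift tables are also laid out by combination. Protocol 10.4.7 likewise asks for change from baseline by dose combination.

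Protocol 6.1.1 gives the sequences. The first reads "Arm A: 5-20 µg/ 40-80 MBq at Visit 2 and 30-45 µg/ 100-140 MBq at Visit 3"; Arms B and C also place 5-20 µg at Visit 2 and 30-45 µg at Visit 3. The second injection follows 15 to 21 days after the first (Protocol 3.1), and iodinated contrast is required at both scans (Protocol 5.2.3).

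Protocol Table 5 marks vital signs and safety laboratory tests at Visits 2 and 3. Its footnote 6 gives the times as "vital signs 0.5, 1, 2 and 4 hours post-injection".

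**The concern.** In a two-injection design reported by combination, a change printed under a combination is naturally read as what happened after that injection. For the first injection the SAP's baseline supports that reading. For the second it does not: the starting point is the state before any study exposure, not the state just before the injection being described.

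Because 30-45 µg is always second, the mismatch is not spread over the cells. It falls on the whole 30-45 µg row and on none of the 5-20 µg row. A shift in creatinine or blood counts that followed the first dose, its contrast or its blood sampling and had not resolved would appear as a change under the higher peptide range. Blood pressure or heart rate in the first four hours after the second injection, where an acute effect would be sought, is compared with a reading from a different day.

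End of Study values are affected most. In completers they follow both doses and both contrast injections, yet the allocation rule puts them only in 30-45 µg cells. Describing safety and tolerability is a secondary objective (Protocol 2.2), and SAP 3.2.2 attaches no caveat to these tables.

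**Working it through.** **1. The plan's own count.** 3 sequences × 8 subjects × 2 injections = 48; 48 / 6 cells = 8 per cell. This matches Protocol Table 3. There is no powered sample size to reproduce.

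**2. Peptide range against visit (Protocol Table 4).**

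| Sequence | Visit 2 | Visit 3 |
|---|---|---|
| A | 5-20 µg / 40-80 MBq | 30-45 µg / 100-140 MBq |
| B | 5-20 µg / 100-140 MBq | 30-45 µg / 160-200 MBq |
| C | 5-20 µg / 160-200 MBq | 30-45 µg / 40-80 MBq |

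The 5-20 µg range has 24 injections at Visit 2 and 0 at Visit 3; the 30-45 µg range has 0 and 24. A matrix with columns for intercept, peptide range and visit has rank 2, not 3, so peptide range and visit order are fully aliased. Each radioactivity range has 8 injections at each visit.

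**3. Age of the reference value.**
- Visit 3 injection, baseline taken on Day 1: 16 − 1 = 15 to 22 − 1 = 21 days.
- Visit 3 injection, baseline taken at screening: screening lies within 2 weeks before randomisation (Protocol 5.2.1), so up to 14 + 21 = 35 days. At Visit 2 the corresponding maximum is 14 days. Protocol 10.1.2 allows screening to be extended, which would lengthen both.
- Next-day laboratory tests, from Day 1: 1 day at Visit 2 (Day 2), and 16-22 days at Visit 3 (Day 17-23).
- End of Study (Day 30-36), from Day 1: 29-35 days.

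**4. What each cell reports.** Let d1 and d2 be the changes caused by the first and second dose with contrast, f the share of d1 still present at Visit 3, and g any drift by then. None of these is in the documents.
- 5-20 µg cells, current rule: d1.
- 30-45 µg cells, current rule: d2 + f·d1 + g.
- 30-45 µg cells, measured from a value just before the second injection: (d2 + f·d1 + g) − (f·d1 + g) = d2.

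With d2 = 0 and g = 0, the current rule prints 0 under 30-45 µg if f = 0, 0.5·d1 if f = 50%, and d1 if f = 100%.

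Now assume no dose effect at all and a common shift D by Visit 3. The 30-45 minus 5-20 µg difference in change equals D: 0.25, 0.5 or 1.0 SD for assumed D of that size. Each radioactivity margin carries (0 + D)/2 = D/2, so D cancels between radioactivity ranges and falls wholly on the peptide comparison. Within the 30-45 µg row the preceding radioactivity range differs by arm, so an equal D in all three cells is itself an assumption.

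**5. The Visit 2 next-day value as a substitute second baseline.** That value contains d1 in full, so the 30-45 µg change becomes d2 + f·d1 + g − d1 = d2 − (1 − f)·d1 + g. With d2 = 0 and g = 0 this is −0.5·d1 at f = 50%, and −d1 at f = 0, where the current rule has no error.

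**6. Residual radioactivity.** 15 × 1440 / 68 ≈ 318 half-lives and 21 × 1440 / 68 ≈ 445, so none remains. What can carry over is a lasting biological effect.

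**7. Is a pre-injection value taken?** Protocol Table 5 marks vital signs and laboratory tests at Visits 2 and 3, and the synopsis safety section lists them at the Baseline Visit on Day 1. The pre-dose list in Protocol 5.2.2 names neither. Footnote 6 and Protocol 5.2.3 time vital signs after injection and on the next day; Protocol 5.2.3 itemises laboratory tests on the next day. If a Visit 3 pre-injection value is recorded, the SAP's allocation rule credits it to the preceding 5-20 µg dose and does not use it as a reference.

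**The case against.** The strongest defence is that a single untreated baseline is a legitimate choice: it shows total change from the state before any exposure. Replacing it outright would hide cumulative effects, and at End of Study a second baseline could make recovery from the first dose look like an effect of the second. This stands, and is why the pre-study baseline should be kept beside the new one.

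The consequence is also bounded. The named safety endpoints (Protocol 3.2.3, SAP 3.1.3) are adverse-event proportions and clinically significant changes recorded as adverse events; they do not use this variable. Nothing is tested, actual values are tabulated beside the changes, and dose selection rests on efficacy endpoints (SAP 3.2.1.1 and 3.2.1.2). The background figures are reassuring: 0.71 µg/kg at the 50 µg maximum, against 1.43 mg/kg within the no-observed-adverse-effect level in rats (Protocol 1.1). All of this stands and limits the weight of the point, but it does not change how the by-combination changes are computed.

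Three stronger readings are tempting and not supported:
- A reader might infer that no pre-injection vital signs are taken, so that the baseline must be a screening reading. The documents leave the timing unclear; they do not show that the reading is absent. A stale screening baseline would also affect Visit 2, not only the 30-45 µg cells.
- A reader might infer that half of the first-dose change is misattributed. The 50% is purely illustrative; f could be zero.
- A reader might infer that a baseline before each injection makes the peptide ranges comparable. It cannot, because peptide range is aliased with visit order whatever baseline is used.

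**Conclusion.** The point holds as one of analysis and presentation. By-combination laboratory and vital-sign changes for all 24 planned 30-45 µg injections, and for End of Study in completers, include any lasting effect of the first dose and contrast plus drift. The 5-20 µg changes do not. At the second injection the reference is 15-21 days old at best, and up to 35 days old if it is a screening value.

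The direction of the asymmetry follows from the text alone. Its size does not: d1, f and g are unknown and may be small. The conclusion assumes the sequences are given as planned and that the tables are read as effects of the combination named in each column. It bears on a secondary, descriptive objective and not on the primary endpoint, but the correction is cheap.

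**What to change.** **SAP 3.2.2, 3.2.2.2 and 3.2.2.3.** For by-combination changes and shift tables at Visit 3, add a change from the last value before the second injection. Keep the pre-study baseline alongside it, including for End of Study and the overall column, so that cumulative change stays visible. Where no Visit 3 pre-injection value exists, leave the per-injection change missing; do not substitute the Visit 2 next-day value. Footnote the tables to say that peptide range is confounded with visit order by design, and that the added column removes only shifts already present before the second injection.

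**Protocol 5.2.2.** State that the vital signs already marked in Table 5 at Visits 2 and 3 include one pre-injection set, and that the Visit 3 safety bloods include a pre-injection sample, drawn with the T0 PK sample. For subjects already past Visit 3 only the SAP change can apply, using whatever pre-injection values were recorded.

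**Cost.** One more derived baseline variable, two baselines to footnote, one vital-sign set per visit if it is not already taken, and possibly one more haematology and biochemistry set at Visit 3, since the laboratory tests itemised in Protocol 5.2.3 fall on the next day.

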3.2.2.1 Adverse events

All AEs will be recorded and graded by investigators using the NCI CTCAE classification (Version 4.03, dated 14 June 2010), will be coded using the MedDRA Version 19.1 or higher, and will be classified by MedDRA PT and SOC.

Listings will be presented and sorted by combination of injected peptide/radioactivity dose range of ⁶⁸Ga-OPS202, subject number, start date of AEs, primary SOC, PT and verbatim text for all adverse events recorded during the study.

Listings of SAEs, AEs leading to IIP withdrawal and AEs leading to death (fatal outcome) will also be presented.

Also, a listing of grade ≥ 3 AEs will be provided.

Treatment Emergent Adverse Events (TEAEs) will be flagged (*) in the AE listings and will be summarised.

A TEAE is defined as any AE that occurs during the study if:

- (1) it was not present prior to receiving the first ⁶⁸Ga-OPS202 injection, or
- (2) it was present prior to receiving the first ⁶⁸Ga-OPS202 injection but the intensity increased during the study, or
- (3) it was present prior to receiving the first ⁶⁸Ga-OPS202 injection, the intensity is the same but the causality became related during the study.
- (4) AEs starting > 28 days after last ⁶⁸Ga-OPS202 injection will not be considered as TEAEs.

An overall summary table of all AEs will be presented by combination of injected peptide/radioactivity dose range and overall.

TEAEs will be summarised by combination of injected peptide/radioactivity dose range and overall with the number and percentage of subjects with adverse events classified by primary SOC and PT. The number of occurrences of a TEAE will also be presented.

In addition, summary tables will also be presented for SAEs, TEAEs by intensity and causality and TEAEs associated with withdrawals.

In the event of multiple occurrences of the same AE (same PT) being reported by the same subject, the maximum intensity (Grade 5 > Grade 4 > Grade 3 > Grade 2 > Grade 1 > missing > not applicable) and the most serious causality (related > missing > not related) will be chosen. Nonetheless, for the table “Overall summary of adverse events”, in the cross classification of causality and intensity, any subject experiencing multiple AEs with different intensities for each causality category will be counted for each intensity.

3.2.2.2 *Laboratory data*

A separate listing of normal ranges for Standard International (SI) units will be provided by gender and age where relevant.

Laboratory data (serum haematology and biochemistry panels, urinalysis) will be listed in SI units and abnormal values will be flagged (high [H], low [L], clinically significant [C], NCI-CTC grade (G)) where applicable. Any unscheduled laboratory assessments will be flagged [U] in the listings.

- **Haematology and Biochemistry**

For haematology and biochemistry parameters, the baseline will be defined as the last measurement collected prior to the first IIP administration.

For haematology and biochemistry parameters, summary statistics, by combination of injected peptide/radioactivity dose range and overall, will be presented at each scheduled assessment (Baseline, Post-dose, EOS/EW) for actual values and changes from baseline.

Shift tables for haematology and biochemistry parameters will be presented of the number and percentage of subjects with low, normal or high values.

Haematological and biochemistry toxicities will be recorded and graded according to the NCI-CTC criteria, Version 4.03, dated 14 June 2010. The NCI CTC grade (0 to 4) of haematology and biochemistry by visit and by subject and will be listed in Section 16.2.8.

Listings of the laboratory parameters (as described in SAP Appendix 2 section 14.3.4) will include listings of NCI-CTC Grade 3 and 4 haematological toxicities, listings of NCI-CTC Grade 3 and 4 biochemical toxicities and listings of out of range biochemistry parameters that could not be graded using NCI-CTC grade (below Lower Limit of Normal range (LLN) – normal – above Upper Limit of Normal range (ULN)).

Those listings will be presented by combination of injected peptide/radioactivity dose range, subject number and visit.

- **Urinalysis**

For categorical urinalysis data (absent/trace/positive of protein, ketones, bilirubin, blood, urobilinogen, nitrites, leukocyte esterase and glucose) frequency tables, by combination of injected peptide/radioactivity dose range, will be presented at each scheduled assessment (Baseline, post-dose, EOS/EW).

For continuous urinalysis data (pH and specific gravity), summary statistics, by combination of injected peptide/radioactivity dose range, will be presented at each scheduled assessment (Baseline, post-dose, EOS/EW) for actual values and changes from baseline.

3.2.2.3 *Vital signs*

Vital signs (body temperature, supine and standing blood pressure and heart rate, respiratory rate) and body weight will be listed by each assessment by combination of injected peptide/radioactivity dose range and subject. Any unscheduled vital signs will be flagged [U] in the listing.

Baseline values will be defined as the last vital signs measurement collected prior to the first IIP administration.

Summary statistics by combination of injected peptide/radioactivity dose range and overall will be presented at each scheduled assessment for actual values and changes from baseline.

Following assessment will be analysed: Baseline, 0.5h Post-dose, 1h Post-dose, 2h Post-dose, 4h Post-dose, EOS/EW.

3.2.2.4 *ECG*

ECG results will be listed at each assessment (Screening, EOS/EW) by combination of injected peptide/radioactivity dose range and subject. Any unscheduled ECG will be flagged [U] in the listings.

Baseline will be defined as the first ECG measurement collected prior to the first IIP administration.

For continuous ECG parameters (heart rate, RR duration, PR duration, QRS duration, QT duration, QTc Bazett, QTc Fridericia, QTc manual) summary statistics, by combination of injected peptide/radioactivity dose range and overall, will be presented at each scheduled assessment (EOS/EW) for actual values and changes from baseline.

For interpretation of clinical significance (within normal limits / abnormal, not clinically significant / abnormal, clinically significant / not evaluable), a frequency table will be presented, by combination of injected peptide/radioactivity dose range and overall, at each post-dose assessment (EOS/EW) as well as the changes from baseline with the following categories: improved, stable, worsened, clinically significant worsening.

3.2.2.5 *Physical examination*

Physical examination (normal, abnormal, specification for abnormal result) will be listed by combination of injected peptide/radioactivity dose range, subject number and visit. Any unscheduled physical examination will be flagged [U] in the listings.

3.2.3 *Missing data and outliers*

3.2.3.1 *Missing data*

- Efficacy endpoints

No imputations will be made for missing data.

- Safety endpoints

If a value requires a retest (for laboratory values, vital signs, ECG), the closest non-missing reliable value to the scheduled visit is used in the summary tables. An assessment is considered reliable if it is performed without any technical problem or altered blood samples and if the result is within the range of plausible values.

Any repeat or additional assessments performed will be included in the individual subject data listings.

For AEs with missing information for the intensity and/or causality, the value will not be replaced and will be summarized as a separate category.

For all other variables, no imputations will be made for missing data.

3.2.3.2 *Missing or incomplete dates*

In all listings, missing or incomplete dates should be left as they have been recorded. However, for calculation / sorting / assignation based on dates, the following methods will be used:

- The most conservative approach will be systematically considered (i.e., if the onset date of an AE/concomitant medication is missing / incomplete, it is assumed to have occurred during the study treatment phase (i.e. a TEAE for AEs) except if the partial onset date or other data [stop date, ...] indicates differently).
- A missing/incomplete date of medical history or disease diagnosis will be assumed to have occurred before any study treatment.
- If a partial date and the associated information do not allow to state about the assignation to a group / category, all the possible groups / categories will be considered (i.e.: an AE could be assigned to several possible doses at event onset according to its partial onset date and stop date. Particularly an AE with missing start date will be assigned to each dose received before its end date. Similarly a medication with partial start and stop dates could be considered as prior and concomitant treatment).
- Where possible, the derivations based on a partial date will be presented as superior inequalities (i.e., for an AE started in FEB2004 after the administration performed on 31JAN2004, the days since last administration will be " ≥ 2 ". Similarly the duration of ongoing AEs or medication will be " $\geq xx$ " according to the start and last visit dates).

3.2.3.3 *Outliers*

Any outlier identified prior to database lock which is impossible/implausible will be excluded from the analysis. For other identified outliers, the impact should be assessed by performing the statistical analysis with the actual values and at least one other analysis eliminating or reducing the outlier effect.

If any outliers are identified after database lock the statistical analysis should be performed with the actual values and at least one other analysis eliminating or reducing the outlier effect.

A search of outliers by Chiltern should be performed before the database lock and actions with the sponsor should be defined (e.g. edition of queries).

3.2.4 *Subject disposition*

The numbers and percentages of subjects included in each of the Screened, Randomised, Safety, PP and PK population will be tabulated in total and by randomisation arm. The reasons for subject exclusions from PP population will also be tabulated.

A listing of dates and time of assessments will be presented by subject for randomisation arm.

A summary table will be presented for each subject population presenting the number of subjects in each randomisation arm at each visit and identifying the number of subjects who withdrew from the study over time. A unique flow chart will be drawn with the number of subjects in each population.

3.2.5 *Withdrawals*

Discontinued subjects will be listed and a summary table of the number and percentage of subjects who completed and withdrew from the study and the reasons for withdrawal will be presented by randomisation arm and overall.

3.2.6 *Demographic and baseline characteristics*

In order to characterise the subjects, descriptive summary statistics (n, mean, SD, median, minimum, and maximum) or frequency counts of demographic and baseline data will be presented by randomisation arm (three sequences) and overall for the following populations:

- Randomised population
- PP population.

No statistical comparison of the randomisation arms will be performed.

Summary statistics will be provided for demographic and baseline characteristics:

- sex, race/ethnicity, age and age class
- height, weight at screening, body mass index (BMI) and BMI in categories at screening (refer to Appendix 1, Derived data)
- Eastern Cooperative Oncology Group (ECOG) performance status

Summary statistics of the tumour characteristics will be provided:

- site of primary tumour
- primary tumour resected
- time since diagnostic (refer to Appendix 1, Derived data)
- type of the tumour (functioning or non-functioning)
- tumour grade according to WHO 2010 classification
- differentiation status
- Tumour, node and metastasis (TNM) staging
- presence of metastases
- time since diagnostic of metastases (see refer to Appendix 1, Derived data)
- location of metastases

Summary statistics for the previous somatostatin receptor scan will be provided:

- time since scan (months)
- number of positive lesions (in total, in liver, in bone, in lymph nodes)

All demographic and baseline characteristics will be listed by randomisation arm and subject. Pregnancy tests performed will be listed by randomisation arm, by subject, and by visit.

3.2.7 *Medical and surgical history*

Medical and surgical history will be coded using MedDRA Version 19.1 or higher.

Listings will present the PT and verbatim text. The listings will be sorted by randomisation arm, subject number, date of diagnosis, primary SOC, PT and verbatim text.

A frequency table of the number and percentage of subjects will be provided for all medical and surgical history by primary SOC and PT for each randomisation arm and overall on the Randomised and PP population.

3.2.8 *Prior Surgical Procedures for GEP-NETs*

Prior surgical procedures for GEP-NETs will be tabulated and listed in a similar way to medical and surgical history.

3.2.9 *Subject compliance*

3.2.9.1 *Subject exposure to IIP*

Subject exposure to IIP will be described using a summary table by randomisation arm, for following data:

- Number of injections
- Exposure duration, as defined in Appendix 1 Derived data

Then, for each of the six combination of injected peptide/radioactivity dose range, a summary table will present the following information using descriptive statistics:

- Injected peptide mass dose (μg)
- Injected radioactivity dose (MBq)

Computational details for actual injected doses (peptide mass dose and radioactivity doses) are available in the Appendix 1 Derived data.

A first listing will present IIP preparation by subject and randomisation arm, with following information:

- Date and time of IIP preparation
- Final prepared volume (mL)
- Final prepared dose of radioactivity (MBq)
- IIP prepared as per protocol (yes/no with reason)

A second listing will be presented for IIP administration, by subject and randomisation arm, with following information:

- Administration performed to the subject (yes/no)
- Date and time of injection
- IIP and batch number
- Volume immediately before administration (ml)
- Radioactivity dose immediately before administration (MBq)
- Left over volume immediately after administration (mL)
- Left over radioactivity dose immediately after administration (MBq)
- Injected peptide mass dose (μg)
- Injected radioactivity doses (MBq)

Moreover, a listing of subjects with extravasation during injection or difficulties during IIP administration will be provided.

3.2.9.2 *Subject compliance*

For each subject, the overall compliance (%) will be calculated as the ratio of the actual number of injections over the planned number of injections, then multiplied by 100 (c.f. in Appendix 1 Derived Data).

A summary table of compliance by randomisation arm and overall will be presented on the Safety population, analysed as a continuous variable. Additionally, the number and percentage of subjects with a compliance in the categories (50% or 100%) will be provided by randomisation arm and overall.

